[figure not shown]
Oyster Point Pharma, Inc.

Clinical Protocol: OPP-003:

**Multicenter, Randomized, Controlled, Double-Masked Clinical Trial
to Evaluate the Efficacy of OC-02 Nasal Spray
on Signs and Symptoms of Dry Eye Disease (The RAINIER Study)**

Statistical Analysis Plan Version 1.0

October 4, 2018

[figure not shown]

CONFIDENTIAL

Oyster Point Pharma, Inc.

**Protocol OPP-003
Statistical Analysis Plan**

October 4, 2018

CONFIDENTIAL

Synopsis

Protocol title	A multicenter, randomized, controlled, double-masked clinical trial to evaluate the efficacy of OC-02 nasal spray on signs and symptoms of dry eye disease (the RAINIER study)
Protocol number	OPP-003
Investigational product	2.0% OC-02 nasal spray
Study objective	To evaluate the safety and effectiveness of OC-02 Nasal Spray as compared to placebo on signs and symptoms of dry eye disease (DED)
Treatment assignment	Approximately 45 subjects will be randomized in a 2:1 ratio to the two treatment groups: placebo, 2.0% OC-02 treatment
Analysis population	Efficacy: the Intent-To-Treat (ITT) population consists of all randomized subjects classified according to the treatment to which they were randomized. Safety: the safety population includes all randomized subjects who received at least one dose of the study drug. Analysis using the safety population will group subjects according to the treatment actually received.
Primary endpoint	Change in Schirmer's Test Score (STS) from baseline to Visit 5 (Day 28)
Statistical method for primary efficacy analysis	[REDACTED]
Sample size and power	[REDACTED]

CONFIDENTIAL

Contents

1. Introduction.....	1
2. Investigational plan.....	1
2.1. Study design.....	1
2.2. Study objectives and outcome measures	1
2.3. Randomization and masking.....	2
3. Study schedule	3
3.1. Study days.....	3
3.2. Unscheduled visits.....	3
4. Analysis populations.....	3
4.1. Intent-To-Treat population	3
4.2. Safety population	4
5. Sample size determination and power calculation	4
6. Protocol deviations.....	5
7. Statistical analysis: general considerations and conventions	6
7.1. Unit of analysis	6
7.2. Definition of time	7
7.3. Missing and partial data.....	7
8. Subject characteristics, disposition, and exposure to study drug	7
8.1. Demographic and baseline characteristics.....	7
8.2. Subject disposition.....	8
8.3. Treatment exposure	9
8.4. Concomitant medications and therapies.....	9
9. Baseline, post-baseline, and unscheduled measurements	9
9.1. Ocular assessments	10

This statistical analysis plan (SAP), which is based on Amendment 1.0 of the study protocol dated 11 July 2018, defines the methods and analyses that Oyster Point Pharma, Inc, (henceforth, Oyster Point) plans to use to analyze the data from Protocol OPP-003. This SAP complies with guidance promulgated by the International Conference on Harmonization (ICH) and the US Food and Drug Administration (FDA). If the protocol is subsequently amended, this SAP may be amended as well. Should the SAP and the protocol be inconsistent with respect to the planned analyses, the language of the SAP is governing.

2. Investigational plan

2.1. Study design

Oyster Point's protocol OPP-003 is a Phase 2, multicenter, randomized, double-masked, placebo-controlled study designed to evaluate the safety and efficacy of OC-02 nasal spray in adult participants with dry eye disease (DED). Subjects with DED who provide signed informed consent and meet enrollment criteria (that is, all inclusion criteria and none of the exclusion criteria) will be randomized in a 2:1 ratio to be treated with OC-02 nasal solution delivered as a 50 microliter (μ L) intranasal spray in each nostril BID for a total of 4 weeks:

- Placebo (vehicle) nasal spray[control]
- 2.0% OC-02 nasal spray[treatment]

All enrolled subjects will receive treatment according to the protocol's schedule of visits and procedures (see Appendix 1). [REDACTED]

[REDACTED]

[REDACTED]

2.2. Study objectives and outcome measures

The Protocol OPP-003 is designed to evaluate the safety and efficacy of 2.0% OC-02 nasal spray compared to placebo in subjects with DED. See Table 1 for the study objectives and outcome measures.

Table 1. Study objectives and outcome measures

Primary

Objective: to determine if 2.0% OC-02 is superior to placebo with respect to change from baseline in Schirmer's Test Score (STS) at Visit 5 (Day 28)

Outcome: change in STS from baseline to Visit 5

Exploratory & Safety

Objective 1: to evaluate the difference in efficacy between 2.0% OC-02 and placebo with respect to [REDACTED]

[REDACTED]

Objective 2: to compare the safety and tolerability of 2.0% OC-02 nasal spray and placebo with respect to the following outcomes:

- Change in best corrected visual acuity (BCVA)
- Slit-lamp biomicroscopy
- Intranasal examination
- Adverse events

2.3. Randomization and masking

Randomization will occur at Visit 1 (Day 1). Each qualified subject will be assigned a subject number in strict numerical sequence at a clinical site; no number will be skipped or omitted. If all inclusion and exclusion criteria are met at Visit 1, each qualifying subject will be assigned a randomization number.

Randomization will be performed electronically once the subject has been deemed eligible for the study. The site staff will give the patient a study kit labeled with a kit number that will correspond to the system-assigned randomization number. The randomization number and kit number will be recorded on the patient's source document and electronic case report form

(eCRF). The Sponsor, Investigators, and study staff will be masked during the randomization process and throughout the study.

3. Study schedule

Subjects are expected to attend 5 visits over the study period of approximately 4 weeks (28 days) of participation in the study. They are examined at screening (Day 1, randomization), Visit 2 (Day 7), Visit 3 (Day 14), Visit 4 (Day 21), and Visit 5 (Day 28). See Appendix 1 for the schedule of visits.

3.1. Study days

Study days will be calculated from the date of randomization, which will be designated as Day 1 (Visit 1). Positive study days will be measured forward in time from randomization while negative study days will be measured backward from randomization (e.g., Day 2 will represent the day after randomization while Day -1 will represent the day before randomization).

3.2. Unscheduled visits

Unscheduled visits may be performed to ensure safety of the subject. The study investigator or designee should record all information gathered at unscheduled visits on the Unscheduled Visit/Early Exit Visit pages of the Source Document and corresponding electronic Case Report Form (eCRF). If a randomized subject does not attend a scheduled visit, the eCRF pages for the missed visit will be skipped. All reasonable efforts should be made to schedule subjects for an Exit Visit to complete Exit Procedures.

4. Analysis populations

4.1. Intent-To-Treat population

The Intent-To-Treat (ITT) population will include all randomized subjects. Analyses using the ITT population will group subjects according to the treatment to which they were randomized. The ITT analyses will be considered the primary analysis population for efficacy outcomes.

[figure not shown]
4.2. Safety population

The safety population will include all randomized subjects who received at least one dose of the study drug. Analysis using the safety population will group subjects according to the treatment actually received. The safety analysis will not exclude any data because of protocol violations.

[figure not shown]
5. Sample size determination and power calculation

The study will randomize approximately 45 subjects in a 2:1 ratio to the two treatment groups. Approximately 28 subjects of the 30 subjects in the 2.0% OC-02 treatment group and 13 of the 15 subjects in the placebo (OC-02 vehicle) nasal spray are expected to complete their assigned treatment and have endpoint assessments at Visit 5.

The primary hypothesis underlying the study is that 2.0% OC-02 nasal spray is superior to the placebo group with respect to mean change in STS from baseline to Visit [REDACTED]
[REDACTED]

6. Protocol deviations

CONFIDENTIAL

Prior to database lock, masked members of study team will review the data for each subject to assess whether an important deviation has occurred. The data management plan will describe the process planned for those reviews.

7. Statistical analysis: general considerations and conventions

Descriptive and inferential statistics will be used to summarize results of Protocol OPP-003.

Continuous variables will be summarized using the number of subjects (n), mean, SD, median, 25th and 75th percentiles, and minimum and maximum. Discrete variables will be summarized using counts and percentages. Baseline measures will be defined as the last measure prior to the initiation of study treatment, usually at Visit 1 screening.

All summaries will be presented by treatment group. Summaries will be provided for demographics, medical history, concomitant medications, and subject disposition. For the summaries of medical history, concomitant medications, and AEs, Medical Dictionary for Regulatory Activities (MedDRA®) and World Health Organization Drug dictionaries, as appropriate, will be used.

All data listings, summaries, and statistical analyses will be generated using SAS® Version 9.4 or higher or other validated software.

The following sections describe the analyses to be used for the study.

7.1. Unit of analysis

For efficacy endpoints, the unit of analysis will be the study eye defined as the eye that meets all inclusion and exclusion criteria. If both eyes qualify, then the study eye will be the eye with the greatest increase in tear production with stimulation by a cotton swab at the Screening Visit. If there is no difference in stimulated tear production, the eye with the lower basal Schirmer's score at screening will be the study eye. If there is no difference for either measure, the right eye will be used as the study eye.

Both eyes will be analyzed for safety variables.

7.2. Definition of time

For visits (or events) that occur on or after randomization, time is calculated in days as:

$$\text{Time} = \text{Visit (or event) date} - \text{Date of randomization} + 1$$

For visits (or events) that occur prior to randomization, time is calculated in days as:

[figure not shown]
$$\text{Time} = \text{Visit (or event) date} - \text{Date of randomization}$$

For listings (e.g., for adverse events), the number of days since first (or last) dose is defined as:

$$\text{Days since first (or last) dose} = \text{Visit (or event) date} - \text{Date of randomization} + 1$$

For summaries that present distribution of time expressed in weeks and months, weeks will be defined as days divided by 7 and months as days divided by 30.4375.

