6.5 Withdrawal Criteria

If at any time during the study the Investigator determines that a subject's safety has been compromised, the subject may be withdrawn from treatment, but will be followed for safety for the duration of the study, unless they refuse to attend follow-up visits.

Subjects may withdraw consent from the study at any time.

Sponsor and/or Investigator may discontinue any subject from study treatment for non-compliance or any valid medical reason during the course of the study (see Section 9.6.2).

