8.1.2 Dispensation Schedule

[figure not shown]
- At Visit 1, qualified subjects will be randomized and the first dose of study drug will be administered in office. The second daily administration will happen at home.
- At Visit 4 subjects will receive their first daily dose of study drug during CAE[®] exposure. The second daily administration will happen at home.
- At Visit 2, Visit 3, and Visit 5 the first daily dose of study drug will be administered in office concurrent with Schirmer's testing. The second daily administration will happen at home.
- Between clinic visits, subjects will self-administer OC-02/Placebo BID as a 50 μ L intranasal spray in each nostril.

[figure not shown]

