9.8 Study Duration

An individual subject's participation will involve 5 visits over approximately 4-weeks (28 days)

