10 SAFETY DEFINITIONS, SAFETY MONITORING AND REPORTING

10.1 Adverse Event

An adverse event (AE) is defined as any untoward medical occurrence associated with the use of a drug in humans, whether or not the event is considered drug-related. An AE can therefore be any unfavorable and unintended sign (e.g., an abnormal laboratory finding), symptom, or disease occurring after the subject started dosing with the study drug, without any judgment about causality. Any pre-existing medical condition that worsens after administration of the study drug will also be considered a new AE.

Study drug includes the investigational drug under evaluation and placebo.

Documentation regarding the AE should be made as to the nature, date of onset, end date, severity, relationship to study drug, action(s) taken, seriousness, and outcome of any sign or symptom observed by the Investigator or reported by the subject upon indirect questioning.

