10.2.2. Exploratory efficacy analysis methods

11. Safety analyses

The safety population will be used for all safety analyses. All recorded safety parameters will be listed.

The investigator will promptly review each Adverse Event (AE) for accuracy and completeness, and classify each AE according to its intensity, its relationship to study drug or administration procedure, and its seriousness. AE will be coded using version 20.1 or later of the MedDRA dictionary. AEs will be monitored throughout the study and documented on the appropriate AE form. AEs will be categorized as ocular and non-ocular as well as by system organ class (SOC) and preferred term (PT), seriousness, severity, and relation to study medications. AEs will be summarized by subject, not event.

All AE presentations will summarize treatment-emergent adverse events (TEAEs) defined as AEs with onset on or after first dose of investigational drug or placebo.

The following presentations of AEs will be generated:

- Overall adverse events summary (including any AEs, ocular AEs, resolved ocular AEs, non-ocular AEs, TEAEs, ocular TEAEs, non-ocular TEAEs, SAEs, treatment-emergent SAEs, treatment-related treatment emergent SAEs, TEAEs by maximum severity, TEAEs by relationship to study drug, AEs leading to treatment/study discontinuation);
- Serious adverse events (SAE) by SOC and PT;
- All ocular AEs by SOC and PT;
- All non-ocular AEs by SOC and PT;
- AEs suspected to be related to the study medication;
- AEs leading to treatment discontinuation.
- AEs leading to study discontinuation.

All AE data will be presented in listings. Selected AEs will be listed for ocular TEAEs, AEs leading to treatment discontinuation, AEs leading to study discontinuation, and AEs related to the study medication. In addition, for the safety population “traffic light” plots will present reported AEs by severity over time by treatment group.

BCVA will be summarized by treatment group and study visit for both study and fellow eyes.

12. Subgroup analysis

13. Appendices

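### SAP 7.2 computes days since last dose from the randomisation date, so any listing that carries the field would show the study day instead

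*SAP*

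**What the plan says.** SAP 7.2 first defines time for visits or events on or after randomisation as event date minus randomisation date, plus 1. It then turns to listings, with adverse events as the example, and says "the number of days since first (or last) dose is defined as" the same expression: event date minus randomisation date, plus 1. One formula therefore serves both the first and the last dose.

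SAP 3.1 already gives that quantity a name: "Study days will be calculated from the date of randomization, which will be designated as Day 1".

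On dosing, Protocol 8.1.2 says that at Visit 1 "qualified subjects will be randomized and the first dose of study drug will be administered in office". Treatment is twice daily for 4 weeks (SAP 2.1), and dosing is still under way at the last visit: "At Visit 2, Visit 3, and Visit 5 the first daily dose of study drug will be administered in office". No readable section of either document gives a different formula for time since last dose.

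**The concern.** A variable named for the last dose should depend on when that dose was given. This one cannot. For every event after randomisation, study day, days since first dose and days since last dose are the same number.

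The SAP also leaves open whether last dose means the final dose of the study or the most recent dose before the event. The formula is wrong under either reading.

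At stake is the reading of any listing that carries the field. Time since last dose is most informative for events off treatment, and the protocol provides for these: a subject may be "withdrawn from treatment, but will be followed for safety for the duration of the study". Events on or after the Visit 5 dose in completers would be affected too. A reader relying on the column would take the study day for the interval since dosing.

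**Working it through.** **Inputs**
- Randomisation is Day 1 (SAP 3.1).
- The first dose is at the randomisation visit, so on Day 1 (Protocol 8.1.2).
- Dosing runs twice daily for 4 weeks (SAP 2.1), with an in-office dose at Visit 5 (Protocol 8.1.2). Visit 5 is Day 28 ±2, that is, Day 26 to 30.
- Let E be the study day of the event and L the study day of the last dose.

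The plan gives a formula but no worked value, so there is no figure to reproduce.

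**Formulas**
- SAP 7.2: E - 1 + 1 = E, whatever L is.
- First dose on Day 1: E - 1 + 1 = E. The SAP value is right.
- Last dose on Day L, keeping the SAP's +1, event on or after the dose: E - L + 1.
- Excess: E - (E - L + 1) = L - 1.

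**Results with the +1 convention**

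| Meaning of last dose | L | E | SAP value | From last dose | Excess |
|---|---|---|---|---|---|
| Final study dose | 1 | 5 | 5 | 5 | 0 |
| Final study dose | 10 | 12 | 12 | 3 | 9 |
| Final study dose, off-treatment follow-up | 10 | 28 | 28 | 19 | 9 |
| Final study dose, Visit 5 early in window | 26 | 26 | 26 | 1 | 25 |
| Final study dose, Visit 5 on target | 28 | 28 | 28 | 1 | 27 |
| Final study dose, Visit 5 late in window | 30 | 30 | 30 | 1 | 29 |
| Most recent dose, same day | 15 | 15 | 15 | 1 | 14 |
| Most recent dose, day before | 14 | 15 | 15 | 2 | 13 |

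The Day 10, 14 and 15 entries are illustrations. The Day 26 to 30 entries follow from the visit window.

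**Other conventions**
- If a same-day event counts as 0, the interval is E - L and the excess is L. For L = 10 and E = 12 the SAP gives 12 against 2, an excess of 10.
- For an event before the final dose, the SAP's rule for dates before the reference date drops the +1, and the excess is again L. For L = 28 and E = 10 the SAP gives 10 against -18, an excess of 28.

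**How many subjects**

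SAP section 5 expects 28 of 30 and 13 of 15 subjects to complete treatment with Visit 5 assessments. That leaves (30 - 28) + (15 - 13) = 4 of 45 who do not, which is a rough guide to how few could have off-treatment follow-up. For completers, "participation will involve 5 visits over approximately 4-weeks (28 days"), so the plain case is an event on the day of the Visit 5 dose. The documents give no event rate, so the number of affected entries cannot be estimated and could be zero.

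**The case against.** The strongest reply is that nothing visible uses the field. SAP section 11 says that all adverse event data will be listed and describes the planned presentations, but it names no column for days since last dose. Treatment-emergent status rests on "AEs with onset on or after first dose of investigational drug or placebo", not on the last dose. On this view the reference to the last dose is an editorial slip that a programmer would query, since it duplicates the time variable. No source information is lost either: the protocol requires that "Documentation regarding the AE should be made as to the nature, date of onset, end date, severity" be recorded, so the interval could be recomputed wherever a last-dose date is held. The size L - 1 also depends on convention.

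Much of this stands, and it limits the point to a minor one. The listing shells are not visible, and SAP 7.3 and 8.4 show only their headings, so use of the field can be neither confirmed nor excluded. It does not remove the error. SAP 7.2 defines the field for listings, gives adverse event listings as its example and states an explicit formula, so programming to specification produces the wrong value. SAP section 1 also makes the SAP's wording prevail over the protocol's on planned analyses. The choice of convention moves the excess from L - 1 to L; it does not change the cause or the direction.

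**Conclusion.** The concern holds, as a minor error in a stated formula. Any listing that reports days since last dose under SAP 7.2 would show the study day. The overstatement is L - 1 days for events on or after the last dose with the SAP's +1 kept, and 25 to 29 days for an event on the day of a completer's Visit 5 dose. Under that convention the value is correct only if the last dose was on Day 1.

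This rests on first dose and randomisation falling on the same day, as Protocol 8.1.2 provides, and on a listing actually carrying the field. In the visible text the primary endpoint, days since first dose, treatment-emergent classification, relatedness and adverse event summaries are unaffected.

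**What to change.** If no listing will report the interval, delete *(or last)* from SAP 7.2. This needs no data.

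If a listing will report it, keep the present formula for the first dose and add a second line: days since last dose = visit or event date - date of last dose + 1. State which dose is meant. If it is the final study dose, report the field only for events on or after that dose. If it is the most recent dose before the event, dates of home doses are needed as well.

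The cost is one line of text and, in the second case, one derived variable. Before choosing, the sponsor should confirm that a last-dose date is collected. The visible text does not settle this: Protocol 12.5.3 covers amounts of drug received, dispensed and returned, and SAP 8.3 plans a summary of exposure duration without a formula. The case report form is not among the documents, so this is something to check, not evidence of a gap.

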7.3. Missing and partial data

8. Subject characteristics, disposition, and exposure to study drug

8.1. Demographic and baseline characteristics

Quantitative variables will be summarized using the number of subjects (n), mean, SD, median, 25th and 75th percentiles, and minimum and maximum. Qualitative variables will be summarized using counts and percentages.

The following demographic and baseline characteristics will be summarized: age, gender, ethnicity, race, and ocular history.

Age in years will be calculated as the integer portion of the following:

$$[(\text{Date of randomization} - \text{Date of birth}) + 1] / 365.25.$$

Unless otherwise stated, percentages will be calculated relative to the number of subjects randomized. All demographic data will be presented.

Summary tables will describe baseline ocular characteristics for each treatment group.

Medical history will be coded using the MedDRA and summarized, for each treatment group, by system organ class (SOC) and preferred term (PT). Medical history may also be listed for all subjects in the ITT. Medical history may be sorted by treatment group and descending overall frequency, by SOC and PT, in the summary tables. Medical history will be presented separately for ocular and non-ocular events.

